9. STATISTICAL CONSIDERATIONS

9.1 Study Design/Endpoints

A single arm, Phase II trial will be performed using combination Cabozantinib and Pembrolizumab in patients with refractory pancreatic cancer. The primary study endpoint is PFS compared to historical PFS.

9.2 Sample Size/Accrual Rate

The historical median PFS for 2nd line metastatic pancreatic cancer will be assumed to be 2.0 months. We hypothesize an improvement in PFS to 4.0 months for this combination regimen.

A sample of 21 evaluable patients will provide 80% power to detect this hypothesized improvement in PFS with 80% power based on a one-sided log-rank test with 5% alpha and an

exponential distribution with an interim analysis plan (Section 9.6). Patient accrual is projected for 24 months with an estimated enrollment of 1 patient per month and 6 months of follow-up after the last patient is enrolled in the trial. Assuming a 5% unevaluable or drop-out rate, a sample of 23 patients will be enrolled in the Phase II trial.

9.3 Stratification Factors

None.

9.4 Analysis of Primary Endpoint

PFS will be estimated using the Kaplan-Meier curve and median PFS and confidence interval will be calculated. The one sample log-rank test will be employed to test improvement in PFS with the combination regimen. Exploratory analysis using the Cox regression model to assess PFS adjusted for a few key clinical parameters will be performed. An intent-to-treat analysis, wherein all patients who received study drug, will be the primary analysis of the PFS outcome.

Given that the timing of radiology scans is every Q8 weeks (+/- 1-2 weeks) or scans as clinically indicated, we will consider the analysis of PFS as interval censored data. The SAS ICLIFETEST will be used for nonparametric survival analysis of interval-censored data while SAS LIFEREG can deal with parametric survival model with both interval and right censored data. The R package for interval censored data (icenReg) which can do nonparametric, parametric and semiparametric Cox models will also be implemented.

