1. OBJECTIVES

1.1 Primary Objective

To measure progression-free survival (PFS), defined as the time from the start of treatment (Cabozantinib + Pembrolizumab combination) until the first documentation of disease progression or death due to any cause, whichever occurs first.

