9.6 Interim Analysis

Interim analysis will be performed based on an optimal two-stage design for Phase II survival trials. Specifically, an exponential distribution with an exact variance estimate of the one-sample log-rank test (OSLT) will be used for the two-stage design (Wu, 2015). Using the R function Optimal.rKJ, this two-stage design assuming an exponential distribution will enroll 14 patients at the first stage. At the time of interim analysis, each patient is followed for an event (disease progression or death) or is censored. If the first stage test statistic $Z_1 < 0.088$, we stop the trial for futility. Otherwise the trial continues to the second stage until a total of 21 evaluable patients is enrolled on the study. The final analysis will be conducted when all patients have been enrolled.

If the second stage test statistic $Z < 1.632$, we don't reject the null hypothesis and conclude no efficacy of the treatment. If $Z \geq 1.632$, we conclude that the treatment is promising.

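### The one-sided 5% alpha of the go/no-go Z in section 9.6 is not assured: its limits suit continuous event times, scheduled scans are 8 weeks apart, and the interval censoring recognised in 9.4 is not carried into Z

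*Combined protocol and SAP*

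**What the plan says.** Section 1.1 runs PFS from the start of treatment "until the first documentation of disease progression or death due to any cause, whichever occurs first". The Study Calendar (section 11) schedules imaging every 8 weeks (±14 days) for the first 6 months and every 12 weeks (±7 days) after that, with extra scans when clinically indicated.

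Section 9.2 states: "The historical median PFS for 2nd line metastatic pancreatic cancer will be assumed to be 2.0 months". The target is 4.0 months, with 21 evaluable patients, one-sided 5% alpha and 80% power.

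Section 9.4 names the test: "The one sample log-rank test will be employed to test improvement in PFS with the combination regimen". It then cites the scan schedule and adds that "we will consider the analysis of PFS as interval censored data". For this it lists software: "The SAS ICLIFETEST will be used for nonparametric survival analysis of interval-censored data", with LIFEREG for parametric models and icenReg for all three model types.

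Section 9.6 holds the decision rule: "an exponential distribution with an exact variance estimate of the one-sample log-rank test (OSLT) will be used for the two-stage design". The trial stops after 14 patients if Z1 is below 0.088, and the treatment is called promising if the final Z is at least 1.632. On the data entering Z, it says that "each patient is followed for an event (disease progression or death) or is censored" and "The final analysis will be conducted when all patients have been enrolled". Section 9.2, by contrast, plans 6 months of follow-up after the last patient enrols.

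**The concern.** A one-sample log-rank Z needs one time per patient. For a progression found on a scan, the documents give an interval (9.4) and a documentation date (1.1), and do not say which enters Z. The documentation date falls at or after the true progression. When scans are about one null median apart, that delay is large relative to the times being tested. If the 2.0 months does not carry the same delay, an inactive regimen looks better than the null.

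Both decisions rest on this Z. A drift upward weakens the futility stop and raises the chance of a false finding of promise. A mismatch the other way costs power. Because the trial is open-label and the convention is not fixed, it could be chosen after results are visible.

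**Working it through.** **Inputs from the documents.** Null median 2.0 and target 4.0 months, 21 evaluable patients, 1 per month, 6 months after the last patient (9.2); 14 then 21 patients, limits 0.088 and 1.632 (9.6); the scan schedule (section 11).

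**Inputs assumed and varied.** Share of events dated exactly (deaths, or scans prompted by symptoms), 0–80%; variance E or (O+E)/2, since the formula is not printed; censoring at the last scan or at the data cut; follow-up cap of 6 months, 12 months or none; interim at the 14th enrolment or 10 weeks later; scan scatter from 0 to ±2 weeks.

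**Step 1: the plan's own figure.** The null hazard is λ0 = ln 2 / 2.0 = 0.3466 per month. With O observed events and E = Σ λ0·t, Z = (E − O)/√E. The two-stage normal calculation with the printed limits gives alpha 0.0504. Power with 21 patients is 0.824 under a 6-month cap and 0.799 under a 5-month cap. Simulated type I error with continuous dating is 3.5–5.4%. Allowing 5% unevaluable, 21/0.95 = 22.1, rounded up to 23. The design is coherent for continuous times.

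**Step 2: what scan dating does to Z.** Take the simplest case: scans exactly 8-weekly, no follow-up cap, no event dated exactly.
- Scan interval: 56/30.44 = 1.84 months.
- Null probability of passing one interval without progression: exp(−0.3466 × 1.84) = 0.5285.
- Mean recorded time: 1.84/(1 − 0.5285) = 3.90 months, against a true mean of 1/0.3466 = 2.89.
- E per patient: 0.3466 × 3.90 = 1.35 instead of 1.
- For 21 events: E = 21 × 1.3525 = 28.4, so a typical null Z is about (28.4 − 21)/√28.4 = 1.39.

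A regimen with no effect then centres near the limit of 1.632 instead of near 0.

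**Step 3: simulation, 2.0 months as a true-time median, documentation dates in Z.** The stage-1 column uses variance E, the interim at the 14th enrolment and caps of 6 or 12 months.

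| Events dated exactly | Type I error | Stop at stage 1 under the null |
|---|---|---|
| All (continuous) | 3.5–5.4% | about 55% |
| 80% | 4–9% | 44–56% |
| 40–60% | 8–24% | 21–44% |
| 20% | 20–36% | 12–21% |
| None | 29–49% | about 5–12% |

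If the final analysis is read at last enrolment, as 9.6 words it, type I error is 3.5–9.5% (80% exact), 6–25% (40–60%) and 25–51% (none).

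**Step 4: 2.0 months as a scan-recorded median on the same schedule.** The true null median is then shorter than 2.0. With 0–80% of events exact:

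| Scan timing | Type I error | Power for a halved hazard |
|---|---|---|
| On schedule | 4–32% | 84–99% |
| ±1 week scatter | 1.6–5% | 79–91% |
| ±2 weeks scatter | 0–3% | 12–86% |

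Power under continuous dating in the same simulation is 85–92%. As a second view, with 20% of events exact, a 6-month cap and censoring at the last scan, true medians of 1.2, 1.4, 1.6 and 1.8 months give type I error of 0.1%, 0.8%, 3.6% and 10.1%.

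**Step 5: do alternatives behave better?** Against a true-time null with the printed limits, one interval-censored exponential score test gave type I error of 2.9–5.6% with power 81–91%. Another variance form gave 5.5–6.7%. Counting deaths after undetected progression as exact events gave 4.7–7.2%. Midpoint dating with the ordinary Z gave 3.6–6.7% (0–40% exact). All come much closer to 5%, but none meets it without calibration.

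**The case against.** Four points deserve weight.

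**The plan knows about interval censoring.** A reader might infer that the issue was overlooked. It was not: 9.4 names it and lists suitable procedures, including a parametric one. What is missing is the link from that paragraph to the Z in 9.6.

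**The direction is unknown.** A reader might infer that alpha is inflated to some particular figure. The documents do not support that. Section 9.1 sets PFS against historical PFS, and section 1.1 defines PFS by documentation, so a like-for-like reading would make 2.0 months a documented median. On that reading, with scatter of 1–2 weeks, the current rule holds 5% in the simulations and the risk is lost power. The historical source is not described, so neither reading can be excluded.

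**The share of scan-dated events is unknown.** It is tempting to say that most progressions will be dated at scheduled scans. No section gives the split, and clinically indicated scans are allowed. At 80% exact, type I error is only 4–9% and the futility stop is little changed.

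**No single replacement test is required.** Step 5 shows that an interval-censored score test also needs calibration. The choice belongs to the trial statistician.

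The conflict over the data cut would exist under any dating rule. It is raised here only because Z depends on it. These objections limit the size and direction that can be claimed. They do not supply the missing convention.

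**Conclusion.** The concern holds in this form: the limits 0.088 and 1.632 correspond to 5% alpha for continuous event times, and the plan does not say how scan-detected progression enters Z, so the stated alpha is not assured. Confidence in that statement is high; confidence in size and direction is low.

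The 29–49%, 8–24% and 4–9% figures require a true-time 2.0 months, documentation dates in Z and an assumed exact share. Under those conditions the null futility-stop rate falls well below 55% unless about 80% of events are exact. If 2.0 months was scan-recorded, the error may fall on either side of 5%, with possible loss of power. This should be fixed before the deciding analysis; it does not call for a larger trial.

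**What to change.** In sections 9.4 and 9.6:

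1. State how the historical 2.0 months was ascertained, and define the null on the same footing as the trial's PFS times. Settle this before choosing the test, without an automatic default to a true-time exponential. If 2.0 months was in fact scan-recorded, an interval-censored score test against that exponential has type I error of 1% or less, but power of only 1–77%.
2. Pre-specify one Z for both looks that respects the scan schedule. Options are an interval-censored exponential score test or a midpoint-dated one-sample log-rank test against a true-time null, or documentation dates against a null built on the same scan schedule. State the event date for scan-detected progressions, unscheduled scans and deaths, and the censoring date, for example the last progression-free scan.
3. Keep 14 and 21 patients. Check 0.088 and 1.632 by simulation under the 8-week ±14-day schedule, including deaths after undetected progression. Recalibrate the limits, or restate alpha and power, if they differ.
4. Reconcile the final data cut: 6 months after the last patient (9.2) or when enrolment is complete (9.6).

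The cost is SAP wording and a short simulation, with no added patients, scans or readers. For the score test, power was about 2 points below continuous dating with symmetric scatter. The loss reached about 6 points in the extreme case of every scan two weeks early and follow-up capped at 6 months.

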9.5 Secondary Endpoints

All patients who received study drugs will be included in the safety analysis. The maximum grade of toxicity for each AE category of interest will be recorded for each patient and the summary results will be tabulated by category and grade. We will describe all serious (\geq grade 3) toxicity events on a patient-by-patient basis. Frequency and incidence tables of toxicity and AEs will be generated.

Other time-to-event endpoints including OS will be estimated using survival analysis methods. Overall response rate and benefit response rate will be estimated along with the exact 95% binomial confidence intervals.

Bioinformatics methods for data processing and data analysis pipelines will be applied and exploratory comparisons of exosomal lipid and organoid cytotoxicity profiles with response and clinical outcomes will be performed using two sample t-test or linear models with control for false discovery rate (FDR).

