1.3 Exploratory / Correlative Objectives

Patient-derived organoids will be developed from archival tumor tissue (if available) and exosomal lipids will be extracted from plasma samples to predict clinical response to Cabozantinib and Pembrolizumab. In order to participate in the correlative studies, patients will be consented on a separate biospecimen collection protocol. This separate consent allows collection of research blood and utilization of archival tumor tissue from patients enrolled in this clinical trial. Participation in correlative studies (organoids and lipids) is optional.

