Figure 6. Lipid profiles are distinct for PDAC versus paired benign tissues while plasma exosomal lipid profiles clearly separate PDAC, precursor lesion (IPMN), and healthy donors. Tissue (A) and plasma exosomal lipids (B, C) were analyzed by Di-nESI-UHR-FTMS. Lipid species in A were assigned based on accurate mass and MS^2 fragmentation patterns using Thermo Lipid Search software. Principal component analysis (PCA) was performed on the exosomal lipids assigned by in-house software PREMISE without (B) or with individual ion intensities normalized to the summed ion intensity of lipids present in 30% of all samples (C). There was clear separation among 60 PDAC (●), 27 IPMN (●), and 38 healthy donors (●) (B, C) and the separation was improved with data normalization (C) with $AUC \approx 0.95-0.97$.

PDOs are three-dimensional *in vitro* models used to study the biology of human cancers and their interactions with the cancer microenvironment. They function as miniature organs with cells that resemble the epithelium of origin by maintaining innate tissue cytoarchitecture, giving rise to distinct cell lineages, and undergoing self-renewal. Importantly, organoids possess all the genetic alterations present in the primary cancer tissues, making them precise genomic models of human cancers and have tremendous potential for predicting *in vivo* drug sensitivity (Boj et al, 2015; Gao et al, 2019; Tiriac et al, 2018). In prior studies, we observed that the results of drug testing in PDOs exactly mirrored the results from patient derived tumor xenografts, which is considered the gold standard cancer model. Since PDOs can be developed and drug tested rapidly, we propose to utilize this model to predict response to the proposed combination therapy. We will also determine if PDO prediction of therapy corresponds to data gathered from plasma exosome analysis.

To carry out these investigations, we will collect liquid biopsies from all patients prior to initiation of therapy and once monthly to determine if we can correlate clinical response to exosomal lipid levels. Methods for this analysis will follow prior investigations (Fan et al, 2018; Lane et al, 2009).

[figure not shown]
[figure not shown]

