Imaging: CT/MRI C/A/P	Within 8 weeks of treatment initiation	CT of the chest, abdomen, and pelvis or CT of the chest with MRI of the abdomen and pelvis will be performed in all subjects at screening and every 8 weeks (± 14 days) after first dose of Pembro/Cabo combination treatment for the first 6-months on-study or as clinically indicated. Upon completion of 6 months on study, these assessments will be performed every 12 weeks (± 7 days) up to 12-months post-treatment initiation. Tumor imaging will continue until either 12-months post-treatment initiation OR until radiographic disease progression per RECIST 1.1 as determined by the investigator. PR or CR per RECIST 1.1 at a given time point must be confirmed by repeat assessments ≥ 4 weeks after the criteria for response are first met.					

Correlative: Blood samples for Exosomal Lipids (optional)	
See ** below. These 7 blood draws for Exosomal Lipids are optional, and will be collected via another biospecimen sample collection protocol.
 
10cc blood in lavender-top tube w/ EDTA will be collected at the following 7 timepoints:
 
Pre-treatment baseline: i.e., predose Cycle 2 clinic visit Cycle 3 clinic visit Cycle 4 clinic visit Cycle 5 clinic visit Cycle 6 clinic visit Cycle 7 clinic visit
 
collected once monthly for 6-months (i.e., at clinic visit during Cycles 2 – 7). The first blood draw is prior to Cycle 1; the second blood draw occurs immediately prior to Cycle 2 (i.e., blood is drawn on day 1 of each cycle, up to Cycle 7).
						
Correlative: Archival Tumor (optional)	
*** If archival tissue is available, tumor tissue will be obtained via another protocol for biospecimen sample collection for correlative, patient-derived organoids. Patients enrolled on this trial will have to sign a separate consent for utilization of archival tissue.
						
Con Meds	X ¹	X ²	X ²	X ²	X ²	X ²	
Adverse Events	≤ 28 days	X	X	X	X	X	
Pembrolizumab (IV infusion)		X, q3 weeks for 8 cycles.		Could continue			
Cabozantinib (oral med)		C1 Day 1 dose given in clinic to monitor safety. C1 D2-D21 doses are taken at home.	X, Daily dose taken at home C2-C8	Could continue			
		Cabozantinib dispensed to subjects every 3 weeks.					
Cabozantinib daily dosing diary		The patient will record the daily amount of Cabozantinib taken in an oral medication log from Cycles 1-8 (i.e., C1D1 to C8D21).					

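### The t-test or linear model named in section 9.5 for the biomarkers does not account for censored PFS/OS or, without a patient effect, for up to seven serial lipid draws per patient

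*Combined protocol and SAP*

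**What the plan says.** Section 9.5 has one sentence on how the biomarkers will be analysed: exploratory comparisons of "exosomal lipid and organoid cytotoxicity profiles with response and clinical outcomes will be performed using two sample t-test or linear models", with FDR control. It does not list the clinical outcomes, say which lipid sample is used, or say how several samples from one patient are combined.

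Elsewhere the plan does use methods that suit censored data:

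- Section 9.5, on the endpoints themselves: "Other time-to-event endpoints including OS will be estimated using survival analysis methods".
- Section 9.4, on PFS: "we will consider the analysis of PFS as interval censored data". It names nonparametric, parametric and semiparametric software for this, and a Cox model for a few clinical covariates.

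Neither section ties these methods to the biomarkers.

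On the data, section 1.3 says that "exosomal lipids will be extracted from plasma samples to predict clinical response". Section 2.5 plans blood before treatment and "once monthly to determine if we can correlate clinical response to exosomal lipid levels". The study calendar (section 11) says "These 7 blood draws for Exosomal Lipids are optional" and places them before treatment and at the visits for cycles 2 to 7. Organoids come from archival tissue (sections 1.3 and 5.1). Section 1.3 adds: "Participation in correlative studies (organoids and lipids) is optional".

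**The concern.** Two features of the data fall outside what a two-sample t-test or an ordinary linear model handles.

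1. **Censoring.** If PFS or OS is among the clinical outcomes, some times are known only to exceed the end of follow-up, and PFS dates are known only to lie between scans. A linear model on observed time treats a censored time as an event time.
2. **Repeated lipid samples.** Up to seven values from one patient are correlated. A t-test or a linear model without a patient term counts them as independent. There is also a timing problem: a lipid value drawn at cycle 5 cannot predict a progression that occurred before it, so on-treatment values must not be related to PFS counted from the start of treatment as if they had been known then.

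FDR control adjusts for testing many lipids. It takes the individual p-values as valid and cannot repair them. What is at stake is the exploratory objective in section 1.3: true associations could be missed, and lipids could be flagged only because each patient was counted several times.

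**Working it through.** **The plan's own figures.** No sample size or power is given for the correlative work. The trial's size, which bounds it, reproduces:

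- 21 / 0.95 = 22.1, rounded up to 23 enrolled, as in section 9.2.
- The stated two-stage rule (14 then 21 patients, cut-offs 0.088 and 1.632, exponential medians 2.0 and 4.0 months, one patient per month) gives one-sided error 0.0504 and power 82.4% with 6 months of follow-up per patient, or 79.9% with 5 months. The follow-up restriction is inferred from section 9.2.

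Biomarker numbers are therefore at most 21 to 23, and fewer if patients decline. The rest uses N = 21.

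**Step 1: how much censoring.** Section 6.5 ends follow-up at 1 year from the start of therapy, and section 9.2 gives 6 months after the last enrolment. With an exponential median of 4.0 months:

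- P(PFS > 12 months) = 0.5^(12/4) = 12.5%
- P(PFS > 6 months) = 0.5^(6/4) = 35%

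**Step 2: cost of ignoring it.** Simulation with one standard-normal baseline marker, log mean PFS rising by a slope of 0.70 per SD (assumed), median 4 months at the average marker value, and two-sided 5%. Linear regression of log observed time is compared with Cox. Only right-censoring is modelled, with exact event dates.

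| All times cut at | Mean linear slope (true 0.70) | Power, linear | Power, Cox | Linear error when true slope is 0 |
|---|---|---|---|---|
| 12 months | 0.58 | 55% | 69% | 4.6% |
| 6 months | 0.45 | 46% | 64% | 5.4% |

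Shrinkage is 1 − 0.58/0.70 = 17% and 1 − 0.45/0.70 = 36%. The false-positive rate stays near 5%, because censoring here is unrelated to the marker. The 6-month row is the extreme case in which nobody is followed for longer.

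**Step 3: cost of pooling serial draws.** With m = 7 draws and within-patient correlation ρ (assumed), the variance of a group mean is understated by the factor 1 + (m − 1)ρ. The approximate actual error is 2[1 − Φ(1.96/√(1 + 6ρ))]:

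- ρ = 0.2: factor 2.2, error 19% (simulated 18%)
- ρ = 0.5: factor 4.0, error 33% (simulated 33%)
- ρ = 0.8: factor 5.8, error 42% (simulated 44%)

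The simulations compare 10 with 11 patients. If draws instead stop at progression, and patients with long and short PFS are compared, the error runs from 14% (ρ = 0.3, median 2 months) to about 33% (ρ = 0.7, median 4 months). Together the range is about 14% to 44%. One mean per patient, with all seven draws available and no time trend, gives 4.7% to 5.1%.

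**Step 4: number of responders.** The documents give no expected response rate. For an assumed rate p, P(at most 1 of 21) = (1 − p)^21 + 21p(1 − p)^20:

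- p = 5%: 72%
- p = 10%: 36%
- p = 20%: 6%

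With 2 responders, t-test power for a 1 SD difference is 25% before any FDR adjustment.

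**The case against.** The stated methods are not wrong for everything they cover. The stated aim is mainly to predict response, which is a category, and a t-test of one baseline value per patient by response group holds its 5% error. Organoids are not sampled serially on treatment, so the repeated-sample problem concerns lipids only. A linear model can include a change score or a random patient effect, and nothing in section 9.5 says that draws will be pooled or PFS split into long and short. Section 2.5 refers to methods in cited work, and collection runs under a separate biospecimen protocol, so more detail may exist that the documents do not show. All of this stands. It limits the point to censored outcomes and serial draws, and makes the pooling figures conditional on a choice that the plan leaves open.

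A reader might go further and infer that the correlative results must be invalid or empty. The documents do not support that:

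- Ignoring censoring costs sensitivity, but did not raise the false-positive rate in step 2.
- Few responders is an assumption: the chance of at most one is 72% at a 5% response rate but 6% at 20%.
- It might be said that late samples exist only for patients doing well. Section 6.2 keeps patients in study visits after treatment stops, so drop-out from sampling is plausible but not established. With draws ending at progression and an assumed common drift of 0.2 to 0.3 SD per draw, even a patient-mean comparison has an error of 15% to 27%. The documents give no basis for that drift, so it is not counted here.

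What remains is that the only analysis sentence for these data omits censoring and within-patient correlation, and permits the unsuitable analysis as readily as the suitable one.

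**Conclusion.** The point holds as a minor gap in an exploratory analysis. For biomarkers against PFS or OS, a linear model is a poorer choice than the survival models that the plan already uses: in the illustration it shrinks a slope by 17% to 36% and lowers power from 69% to 55% (12-month cut-off) or from 64% to 46% (6-month cut-off). For serial lipids, pooling draws as independent would raise a nominal 5% error to about 14% to 44%, and FDR control does not address this. These sizes rest on N = 21, exponential PFS, an assumed slope of 0.70 per SD, censoring unrelated to the marker, and within-patient correlations of 0.2 to 0.8. They also rest on reading the clinical outcomes in section 9.5 as including PFS and OS, which that sentence does not spell out. No primary or secondary conclusion and no stopping rule depends on this analysis.

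**What to change.** Replace the sentence in section 9.5 with text to this effect, before outcomes are compared with the biomarkers:

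- Baseline lipid and organoid measures are related to PFS and OS by Cox regression, or for PFS by the interval-censored model already named in section 9.4.
- On-treatment lipids are analysed with a mixed model that has a patient random effect. They are related to later PFS only from a landmark (the first scheduled scan is a natural one) or as a time-dependent covariate.
- The t-test is kept for one baseline value per patient by response group, and reported descriptively if responders are very few.
- FDR control is kept.

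The cost is a few lines of statistical text and a little more programming. No new data, visits or patients are needed.
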